## 12.9. Appendix 9: Medication Adherence Platform

After the device confirms proper treatment ingestion, video recordings will be encrypted and transmitted to a secure centralized location for further analysis, including testing for duplicate enrolment. The captured data and video is reviewable through a roles and rules restricted system ensuring privacy of the information. All video images and data captured by the AiCure application will be held in encrypted format, both within the application itself and on the secure servers used to validate the Study; those servers are located in the U.S., and therefore your data will be stored and processed in the U.S. The system has been designed to support compliance with applicable regulations to protect the privacy and security of healthcare information, including the Data Protection Act 1998.

Phone numbers of the participants may also be collected and stored in an encrypted manner. Storing the phone numbers will allow for direct communication with participants, including automated messaging from the Platform device and contact by healthcare providers or other monitoring personnel. At no time is the phone number visible to healthcare providers or monitoring personnel. Individuals outside the clinical sites will not be provided with participant names, nor will they be given access to participant medical records.

The Platform Provider will protect participants' personal information to the full extent required by law. However, information from this Study, including de-identified video recording(s) of participant performance of various actions, may be submitted to the Study site, and potentially to the U.S. Food and Drug Administration (FDA). Both information obtained by the application, and information in the participant Informed Consent, may be examined by the Study site or the Study site's representatives, and may also be reviewed by the FDA and other regulatory agencies, Institutional Review Board(s) and or Ethics Committee(s). A depersonalized version of the Study data may be generated and retained by the Platform Provider for use beyond the term of the trial. This will be utilized solely to improve the operation of the Platform, categorize adherence activity by disease state or other useful categories, and/or for regulatory filings by the Platform Provider to support future applications for the Platform Provider's product. Individuals who are not associated with the care and treatment of participants will not have access to participant identity or any medical records. The Platform Provider may also retain a copy of Study data in disaggregated (ie identifiable participant) format beyond the term of the trial for the above purposes where the relevant participant has provided express written authorization for the Platform Provider to do this. Any such authorization shall be entirely voluntary on the part of the participant and separate from participation in the Study.

1. INTRODUCTION

The purpose of this reporting and analysis plan (RAP) is to describe the analyses to be included in the Clinical Study Report for Protocol

Revision Chronology:		
2017N314013_00	16-MAY-2017	Original

2. SUMMARY OF KEY PROTOCOL INFORMATION

2.1. Changes to the Protocol Defined Statistical Analysis Plan

Protocol	Reporting & Analysis Plan	
Statistical Analysis Plan	Statistical Analysis Plan	Rationale for Changes

 Enrolled - All participants who sign informed consent 	
 Enrolled - All participants who sign informed consent and for whom a record exists on the study database 	
 Align with standard Enrolled population definition.

 Randomised 	
 mITT population defined to be used for selected displays 	
 Used for key displays

 Primary completer 	
 Population definition refined 	
 To allow for missing data and increase clarity

 Safety 	
 mITT population used for safety reporting 	
 Safety population not required.

 PK population 	
 PK population defined 	
 Used for PK displays

 Endpoint - Model specific PK parameters of danirixin (e.g., oral clearance, oral steady state volume of distribution). 	
 Danirixin concentration and standard pharmacokinetic (PK) parameters for danirixin (e.g. AUC, Cmax, tmax) 	
 Updated due to small number of participants with PK data

 Endpoints - serum IL-8 or sputum mucin 	
 Removed 	
 Not collected

 Primary analysis Bayesian 	
 Primary analysis Frequentist 	
 The primary analysis has been simplified as the historical data could not be used as a prior.

 Modified Primary Completer 	
 Population defined 	
 Defined to allow for a sensitivity around the definitions of quality for the samples

2.2. Study Objective(s) and Endpoint(s)

Objectives	Endpoints
Primary Objectives	Primary Endpoints

 To assess the change from baseline in NETs formation in participants with COPD following 14 days of treatment with danirixin hydrobromide (HBr) 35mg twice daily 	
 Reduction in sputum NETs (quantified by Histone-elastase complexes)
Secondary Objectives	Secondary Endpoints

 To assess the change from baseline in NETs formation in participants with COPD following 14 days of treatment with danirixin HBr 35mg twice daily 	
 Reduction in sputum NETS (quantified by Deoxyribonucleic acid [DNA]-elastase complexes) Reduction in sputum NET area quantification by microscopy

 To further characterize the safety of danirixin HBr 35mg tablets compared with placebo in participants with COPD 	
 Adverse events Vital Signs ECG Spirometry

 To assess the effects of danirixin HBr 35mg twice daily on NETosis-associated biomarkers in sputum and peripheral blood 	
 Change from baseline in sputum resistin levels Change from baseline in the ratio of sputum NETs to sputum neutrophils Change from baseline in sputum elastase activity Change from baseline in peripheral blood neutrophil NET formation (DNA release)

 Characterise the population pharmacokinetic (PK) profile of approximately 14 days of dosing of danirixin HBr 35mg twice daily in participants with COPD 	
 Danirixin concentration and standard pharmacokinetic (PK) parameters for danirixin (e.g. AUC, Cmax, tmax)
Exploratory Objectives	Exploratory Endpoints

 To explore the relationships between NETs formation and lung microbiome composition 	
 Characterize sputum microbiome composition and diversity

 To explore volatile organic compound (VOC) profile in participants with COPD 	
 Characterize relationship between lung microbiome and exhaled volatile organic compounds (VOCs) in stable COPD To explore variability of exhaled VOCs

 To explore the effects of danirixin 	
 Changes from baseline in ex-vivo neutrophil

Objectives	Endpoints
HBr 35mg twice daily on neutrophil activity and exploratory biomarkers	phagocytosis of bacteria by flow cytometry • Changes in exploratory urine, sputum and blood biomarkers (e.g. plasma fibrinogen, serum C-reactive protein)

2.3. Study Design

Overview of Study Design and Key Features	
<pre> graph LR A[30 days Screening period] --> B((R)) B --> C[Placebo, BD (~6 participants)] B --> D[Danirixin 35mg BD (~18 participants)] C --> E[14 days] D --> E E --> F[Early Withdrawal / Follow-up] </pre>	

*R=Randomization
 
Notes:
 
 • Early Withdrawal visit to occur as soon as possible (ASAP) after decision to withdraw by either investigator or participant • Follow up phone-call to occur within 7 days of last dose of study medication 	
Design Features	
 • Single centre, randomized, double-blind, sponsor open, placebo-controlled, 14-day mechanistic study evaluating the effect of danirixin in reducing NET formation.
Dosing	
 • Study treatment will be administered twice daily for 14 days.
Treatment Assignment	
 • Participants will be randomized (3:1) to receive either danirixin HBr 35mg or placebo. • GSK RandAll NG used to generate randomisation schedules.
Interim Analysis	
 • No formal interim analysis will be performed

2.4. Statistical Hypotheses / Statistical Analyses

The objective of this study is to assess whether danirixin impacts NET formation in participants with COPD. There will be no formal hypotheses tests and significant tests. Model based results for the primary endpoint of reduction in sputum NETs (quantified by Histone-elastase complexes) adjusted for baseline, will be used.

3. PLANNED ANALYSES

3.1. Interim Analyses

There is no formal interim analysis planned for this study. Although, blinded data looks were performed at 12 participants and 19 participants. The purpose of the data looks is to check data quality. The data showed that 6 participants had poor quality data. The team decided to replace all 6 participants; approximately 30 participants will be enrolled.

3.2. Final Analyses

The final planned primary analyses will be performed after the completion of the following sequential steps:

1. After decision to terminate DNX in COPD the study was stopped early. 19 subjects had completed the study.
2. All required database cleaning activities have been completed and final database release (DBR)
3. All criteria for unblinding the randomization codes have been met.
4. Randomization codes have been distributed according to RandAll NG procedures.
5. Database freeze (DBF) has been declared by Data Management.

4. ANALYSIS POPULATIONS

Population	Definition / Criteria	Analyses Evaluated
Enrolled	All participants who sign informed consent and for whom a record exists on the study database. This population will be used for the tables/listings of reasons for withdrawal before randomization and listings of AEs and SAEs for non-randomized participants.	
 • Subject Disposition • Reasons for withdrawal before randomization. • Inclusion, exclusion, and randomization criteria deviations
Modified ITT	All randomized participants who receive at least one dose of study treatment. Participants will be analysed according to the treatment they actually received. If a participant received more than one treatment during the treatment period, they will be reported according to the treatment taken the most based on doses taken from each container.	
 • Study population • Efficacy • Safety
Primary Completer	All participants in the Modified ITT population who have completed the assessments supporting the primary endpoint (sputum NETs). 
 • In the case where the modified ITT and the primary completer population are the 	
 • Sputum NETs • Secondary NETs analyses

Population	Definition / Criteria	Analyses Evaluated
	
same, the primary completer population will not be defined and all output will be done on the Modified ITT population.
 
 Participants need sputum samples of acceptable quality at screening/baseline and day 14. Acceptable quality samples have viable leukocytes >50% and coded as acceptable or good in MISPQL 	
Modified Primary Completer	
All participants in the Modified ITT population who have completed the assessments supporting the primary endpoint (sputum NETs).
 
 In the case where the modified ITT and the primary completer population are the same, the primary completer population will not be defined and all output will be done on the Modified ITT population. Participants need sputum samples of reasonable quality at screening/baseline and day 14. 
Reasonable quality samples have viable leukocytes >50% and coded as acceptable, good or poor quality in MISPQL This population will only be use if this increases the available sample from the Primary completer population by 20%.
	
 Secondary NETs analyses
PK	
All participants in the mITT population who had at least 1 non-missing PK assessment (Non-quantifiable [NQ] values will be considered as non-missing values) obtained and analysed whilst on treatment with danirixin.
	
 PK

NOTES : Please refer to [Appendix 11: List of Data Displays](#) which details the population to be used for each displays being generated.

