# 10.2. Populations for Analyses

Population	Description		
Enrolled	All participants who sign the ICF		
	This population will be used for tables/listings of reasons for withdrawal before randomization and listings of AEs and SAEs for non-randomized subjects.		
Randomized	This population (also considered as the Intent-to-Treat (ITT) Population) will consist of all subjects randomized to treatment who receive at least one dose of study medication. This will constitute the primary population for all analyses.		
Primary Completer	This population will consist of all subjects in the Randomized population who have completed the assessments supporting the primary endpoint (sputum NETs).		
Safety	All participants in the Randomized population who take at least one dose of study treatment. Participants will be analyzed according to the treatment they actually received.		

• For purposes of analysis, the following populations are defined:

- Subjects who withdraw from the study and are replaced will be part of the Enrolled, Randomized and (if applicable) Safety populations.
- The primary analysis for the study (mean reduction in sputum NETs) will use the Primary Completer population.

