7.1.3. Population of Interest

The primary efficacy analysis will be based on the Primary Completer population, unless the primary completer populations is the same as the mITT population. In that case the mITT population will be used for all analysis. Participants with poor quality sputum samples should also be excluded from the analysis.

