12.11.11. Non-ICH Listings

Non-ICH: Listings					
No.	Population	IDSL / Example Shell	Title	Programming Notes	Deliverable [Priority]
NETs					
31.	Primary Completer		Listing of NETs	Include Change from Baseline	SAC [2]
32.	Primary Completer		Listing of the Ratio of Sputum NETs to Sputum Neutrophils	Include Change from Baseline	SAC [2]
33.	mITT		Listing of Peripheral Blood Neutrophil NETs Formation	Include Change from Baseline	SAC [2]
34.	Primary Completer		Listing of Sputum Quality Measures	Quality measure, viability of leukocytes, and Squamous epithelial cells	SAC [2]
Spirometry					
35.	mITT		Listing of Spirometry	Include Change from Baseline	SAC [2]
36.	mITT		Listing of Baseline CAT	Flag to indicate if they are part of the primary completer population	SAC [2]
Exploratory					
37.	mITT		Listing of Treatment Adherence		SAC [2]
38.	mITT		Listing of VOCs		SAC [2]
Biomarker					
39.	Primary Completer		Listing of Sputum Resistin	Include Change from Baseline	SAC [2]
40.	Primary Completer		Listing of Sputum Elastase	Include Change from Baseline	SAC [2]
41.	mITT		Listing of Ex-Vivo Neutrophil Phagocytosis of Bacteria by Flow Cytometry	Include Change from Baseline	SAC [2]

Non-ICH: Listings					
No.	Population	IDSL / Example Shell	Title	Programming Notes	Deliverable [Priority]
42.	mITT		Listing of Blood Biomarkers	Include plasma fibrinogen and serum C-reactive protein. Include Change from Baseline	SAC [2]
PK					
43.	PK	PKCL1P	Listing of Danirixin Whole Blood Pharmacokinetic Concentration-Time Data		SAC [2]
44.	PK	PKPL1P	Listing of Derived Danirixin Whole Blood Pharmacokinetic Parameters		SAC [2]

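### The primary analysis applies a Day 14 sputum-quality rule that the protocol does not contain, and no ungated display shows the sputum NETs of the participants it removes

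*SAP*

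**What the plan says.** Protocol section 10.2 defines the Primary Completer population by completion alone: "This population will consist of all subjects in the Randomized population who have completed the assessments supporting the primary endpoint (sputum NETs"). It sets no condition on viability or grade.

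SAP section 4 adds one: "Participants need sputum samples of acceptable quality at screening/baseline and day 14". The standard is then given as "Acceptable quality samples have viable leukocytes >50% and coded as acceptable or good in MISPQL". SAP section 7.1.3 ties the primary analysis to this set: "The primary efficacy analysis will be based on the Primary Completer population, unless the primary completer populations is the same as the mITT population". It repeats the exclusion without naming a visit: "Participants with poor quality sputum samples should also be excluded from the analysis".

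The change table in SAP section 2.1 explains the refined definition as "To allow for missing data and increase clarity". SAP section 3.1 reports, as past events, blinded looks at 12 and 19 participants made to check data quality, and their result: "The data showed that 6 participants had poor quality data".

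SAP section 5.2 lets the screening sample stand in for a failed Day 1 sample. No substitute is offered for a failed Day 14 sample.

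SAP section 4 also defines a Modified Primary Completer population. It re-admits samples graded poor, keeps the 50% viability threshold, and is used only if it enlarges the Primary Completer sample by 20%.

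**The concern.** Day 14 quality is observed after randomisation, in the same visit's sputum as the primary outcome. If treatment can influence whether a sample passes, the participants kept in the two arms are no longer comparable, and the within-arm danirixin change also depends on who passes.

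Two features of the plan add to this. The model in SAP section 7.1.5.1 is a repeated-measures model with a day term, and section 7.1.2 reports Days 7 and 14. Removing a participant for a failed Day 14 sample therefore discards a Day 7 value that the model could use. The same section allows placebo to be dropped for small cell size. The result would then be an uncontrolled change in participants selected partly on Day 14 quality.

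SAP section 7.1.4 states that no intercurrent events are of interest and that endpoint data will be complete in the chosen population. That is so only because those who fail are taken out. At stake is whether a reader can see how far the primary result depends on the restriction.

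**Working it through.** **Inputs.** Target of 24 evaluable participants with 3:1 allocation (Protocol section 10.1); 6 called poor quality and enrolment then put at about 30 (SAP section 3.1); 19 completers when the study stopped (SAP section 3.2); the 20% gate (SAP section 4).

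**The plan's own figure.** 24 + 6 replacements = 30, which reproduces the revised enrolment.

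**How many could be lost, and what opens the gate.** Assume that all 6 fail the rule. SAP section 3.1 does not give the denominator, the visit or the criterion failed, so three denominators are shown.

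| Denominator | Excluded | Kept | 20% of kept | Re-admitted participants needed |
|---|---|---|---|---|
| 19 | 6/19 = 32% | 13 | 2.6 | 3 of 6 |
| 24 | 6/24 = 25% | 18 | 3.6 | 4 of 6 |
| 30 | 6/30 = 20% | 24 | 4.8 | 5 of 6 |

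With 19 completers, if 0 to 2 of the 6 are graded poor but have viability above 50%, none of the excluded is displayed. If 3 to 6 are, those are displayed and the remaining 3 to 0 are not. Thirteen participants at 3:1 leave 13/4 = 3.25, about 3, on placebo. At equal SD the standard error on 13 is sqrt(19/13) = 1.21 times that on 19.

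**Sputum NETs displays (SAP sections 12.11.5, 12.11.6 and 12.11.11).**

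- Adjusted model, Table 2.1 and Figure 2.1: Primary Completer only.
- Unadjusted, Tables 2.2 and 2.4 and Figures 2.2, 2.4, 2.5 and 2.7: Primary Completer only.
- Table 2.3 and Figures 2.3 and 2.6: Modified Primary Completer, unadjusted, gated.
- Listing 31 (NETs values) and Listing 34 ("Listing of Sputum Quality Measures"): Primary Completer only.
- Table 2.11: sputum quality in mITT, with no NETs values.

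Participants with viability of 50% or less are therefore in no sputum NETs display, and no excluded participant's sputum NETs values are listed. SAP section 12.7.1 promises listings for withdrawn participants unless otherwise specified, but Listing 31 specifies Primary Completer.

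**Illustration of possible bias (assumed values throughout).** Take log NETs with SD 1, an absolute correlation r of 0.3 to 0.5 with a latent quality score, and a placebo pass rate of 13/19, about 68%. Let danirixin's pass rate be 85% or 55%. Selection at pass rate p moves the mean by r × phi(z)/p, where phi is the standard normal density and z the normal quantile for p.

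- At r = 0.5 the terms are 0.263 (p = 0.68), 0.137 (p = 0.85) and 0.360 (p = 0.55). The arm contrast moves by 0.263 − 0.137 = 0.126 or 0.360 − 0.263 = 0.097, in opposite directions.
- At r = 0.3 the corresponding shifts are 0.075 and 0.058.
- On the ratio scale these are about 6% to 13%. The sign also reverses with the sign of r.
- The protocol's planning value of 0.7 is log(0.7) = −0.357, and 0.126/0.357 = 0.35.
- For scale, the 95% half-width of the arm contrast with 10 and 3 participants (df 10) is 2.228 × sqrt(1/10 + 1/3) = 1.467 SD, and 0.126/1.467 = 0.09.

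**The case against.** The case against has real force.

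- Excluded participants are not hidden. Table 2.3 and Figures 2.3 and 2.6 are planned, and SAP section 2.1 presents the modified population as a sensitivity around the quality definitions. Listing 8 and Table 1.10 show who is excluded and how many, Table 2.11 shows quality in mITT, and SAP section 12.7.2 requires reasons in the study report. A reader might infer that no display carries the excluded NETs values; these three displays contradict that. What stands is that they are gated, unadjusted and closed to viability of 50% or less.
- A reader might infer that the rule was chosen after seeing results. The documents do not support this: the looks were blinded and concerned data quality, and the rule is undated. One can say only that it is first documented in a SAP that reports the looks as past.
- A reader might infer that danirixin alters sputum quality. The protocol says that it inhibits neutrophil trafficking and is meant to reduce NET formation, but nowhere that it changes leukocyte viability or grade. The mechanism is possible but not shown.
- The 6 may include baseline failures, which are not post-treatment selection and may be rescued by the screening sample. The number failing at Day 14 is unknown.
- This is a small estimation study with no formal tests (SAP section 2.4), and its primary endpoint is worded for danirixin (SAP section 7.1.1). The illustrated shift is under one tenth of the half-width and concerns mean log NETs, whereas the model analyses log change adjusted for baseline.

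These points limit severity. They do not supply the missing analysis.

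**Conclusion.** The concern holds in limited form; severity is should-fix. The primary analysis carries a sample-quality restriction absent from the protocol, and its Day 14 part is a post-randomisation selection with no substitute sample and with loss of usable Day 7 data. A restriction to good samples is defensible. The gap is that its effect on the adjusted result cannot be seen.

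Up to 6 of 19 (32%) are lost if all 6 are completers and all fail, or 25% or 20% on denominators of 24 or 30. The 6% to 13% shift is only an illustration: nothing in the documents fixes its inputs, and the size and direction of any actual bias are unknown. The stated rationale of missing data and clarity does not tell the reader that observed data can be removed on quality grounds.

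**What to change.** 1. In SAP sections 7.1.3, 12.11.5 and 12.11.6, add an ungated sensitivity run of the Table 2.1 / Figure 2.1 mixed model on all mITT participants with a baseline and at least one post-baseline histone-elastase value, whatever the grade. Report it beside the Primary Completer result, with no formal decision rule, in keeping with the plan's estimation approach. State which baseline is used when neither the Day 1 nor the screening sample passes.
2. Change Listings 31 and 34 to mITT, with sample-quality and population flags.
3. Correct the rationale in SAP section 2.1 to say that a sample-quality restriction, absent from the protocol, was introduced.

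The cost is one re-run of an existing program, two listing population changes and a line of text. The downside is that the added estimate includes noisier samples, so it should be read as a sensitivity result. The quality-restricted analysis can remain primary.
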